## 4 ANALYSIS POPULATIONS

Enrolled Population: Defined as all participants who sign an informed consent. The Enrolled Population will be used for summaries of enrollment and participant disposition.

Safety Population (SAF): Defined as all participants who receive any intratumoral administrations of Ad/PNP or any infusion of F-araAMP. The SAF will be the primary population for all safety reporting.

Efficacy Evaluable Population: Defined as all participants who receive at least three intratumoral administrations of Ad/PNP and any infusion of F-araAMP. The efficacy evaluable population will be used as the primary analysis population for all efficacy reporting.

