Subjects will receive a total of 2×10^{11} VP Ad/PNP per injection (3 injections per cycle) distributed across the injected tumors and volume of vector will vary dependent upon estimated tumor volume using the tumor's two dimensions measured by calipers as described in the Operating Procedure - Injection of Investigational Product into the Tumors of Human Subjects. For example, for a subject with 3 tumors of 1.5 ml, 3 ml, and 5 ml size each, 2×10^{11} VP Ad/PNP will be suspended in 3.5 mL and tumors injected with 0.5 mL, 1.0 mL, and 2.0 mL, respectively. If the tumor mass is very large or the total volume for all discreet tumors exceeds 16 ml, a portion of the tumor mass or certain discrete tumors will be selected by the physician and injected with 5 ml of Ad/PNP. The same tumors will be injected with each administration of 5 ml Ad/PNP.

Lesion Volume	Injection Volume
> 16 ml	5.0 mL
12 ml to 16 ml	4.0 mL
8 ml to 12 ml	3.0 mL
4 ml to 8 ml	2.0 mL
2 ml to 4 ml	1.0 mL
Less than 2 ml	0.5 ml

Using aseptic technique, the Ad/PNP solution will be injected percutaneously with injection at multiple sites within the tumor to achieve thorough infiltration. A subcutaneous injection of local anesthetic may be used, if desired.

Approximately 24 to 36 hours following the third administration of Ad/PNP into the tumor (Day 3), subjects will receive 25 mg/m^2 F-araAMP daily for 3 days. F-araAMP will be prepared and administered intravenously over approximately 30 minutes per the package insert. Subjects who do not receive all three administrations of Ad/PNP will not receive F-araAMP; all subjects will be assessed for safety at the scheduled study visits. Subjects who do not receive all three full doses of Ad/PNP may be eligible to receive subsequent doses of F-araAMP at the discretion of the investigator.

In this study, each 5-day course of treatment will commence every 28 days +/- 3 days and subjects will receive up to 5 cycles of Ad/PNP-F-araAMP. The 28-day interval complies with the recommended dosing schedule between courses of F-araAMP used to treat hematological malignancies. Treatment will be discontinued prior to 5 cycles in the event of injected tumor progression (and/or the investigator determines the patient may no longer stand to benefit from further

treatment) or if there is no tumor present for injection. In the event that treatment is discontinued, the subject should complete the Day 28 and Day 56 visits of the last treatment cycle.

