12. STATISTICAL CONSIDERATIONS

12.1 Sample Size

This study is an open-label, multisite, Phase 1/2 study evaluating the safety of repeat administration of a single dose level Ad/PNP-F-araAMP in subjects with head and neck cancer and who have failed or exhausted all standard or approved therapies. No formal sample size estimation will be conducted. Approximately 10 to 20 subjects will be enrolled into the study in order to have 10 subjects evaluable for efficacy; this number of subjects is sufficient to assess preliminary safety and activity to guide design of subsequent clinical studies. This study is to be conducted at Stanford University, Emory University, and Thomas Jefferson University.

A total of 10 to 20 subjects in the safety population provides sufficient precision to rule out a treatment-related SAE rate of 38.5% or more using a one-sided 80% upper confidence limit as per the following table:

Safety Population N	N of Events	Observed Proportion of Events	One-sided 80% Upper Confidence Limit
10	2	0.2000	0.38094
11	2	0.1818	0.35005
12	2	0.1667	0.32382
13	3	0.2308	0.38397
14	3	0.2143	0.35917
15	3	0.2000	0.33735
16	4	0.2500	0.38452
17	4	0.2353	0.36388
18	4	0.2222	0.34528
19	5	0.2632	0.38418
20	5	0.2500	0.36646

With 10 subjects evaluable for efficacy, there is 83% power to reject a null hypothesis ORR of 10% or less when the alternative hypothesis ORR is at least 40% using a one-sided exact binomial test with a target alpha level of 10% (actual alpha is 7%). The null hypothesis is rejected if 3 or more responses are observed (i.e., observed ORR is at least 30%) and is considered sufficient evidence of efficacy to warrant further study of the treatment.

An alternative hypothesis ORR of at least 40% in this study with five cycles of therapy is considered reasonable based on the published phase I results, where 66.7% of subjects in the higher dosing cohorts achieved a BOR of CR or PR with a single cycle of treatment.

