## 6.2 Efficacy

Efficacy analyses will be conducted on the Efficacy Evaluable Population (refer to section 4).

In addition to the tabular summaries detailed below, efficacy data will be provided in by-participant data listings.

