##### **Objective Response Rate**

Separately for injected tumors and overall (per RECIST v1.1), the objective response rate (ORR) is defined as the number of participants who exhibit a BOR response of CR or PR during the up to 5 cycles of treatment divided by the number of participants in the efficacy evaluable population.

Separately for injected tumors and overall (per RECIST v1.1), the ORR will be presented; corresponding two-sided 95% Clopper-Pearson exact confidence intervals (CIs) and the underlying number of participants will also be provided. The efficacy analysis of primary focus will be the analysis of ORR for injected tumors.

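### Every efficacy result, including the ORR behind the 3-response threshold, rests on a subset defined by treatment received, with no supportive analysis in all treated subjects

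*SAP*

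**What the plan says.** SAP section 4 defines two sets of dosed subjects. The Safety Population is "all participants who receive any intratumoral administrations of Ad/PNP or any infusion of F-araAMP", and its stated use is safety reporting. The Efficacy Evaluable Population is "all participants who receive at least three intratumoral administrations of Ad/PNP and any infusion of F-araAMP", and "The efficacy evaluable population will be used as the primary analysis population for all efficacy reporting". SAP 6.2 and the Secondary Efficacy Analyses heading repeat that efficacy is analysed on the evaluable set. The Objective Response Rate text takes the number of responders "divided by the number of participants in the efficacy evaluable population". The protocol has the same population in its synopsis and in section 12.6. SAP section 4 calls the evaluable set primary, but no second efficacy population is named and no sensitivity analysis is described.

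On numbers, protocol 12.1 says: "Approximately 10 to 20 subjects will be enrolled into the study in order to have 10 subjects evaluable for efficacy". The same section also applies the range to dosed subjects: "A total of 10 to 20 subjects in the safety population". Protocol 12.1 and SAP 3.3 then set the efficacy criterion. Three or more responses among 10 evaluable reject an ORR of 10% and count as enough evidence to study the treatment further.

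Within the evaluable set, missing data are handled cautiously. A participant with no post-baseline response result is classed as not evaluable (NE) for BOR and stays in the ORR denominator. For durable response, SAP 6.2.2.1 counts those who discontinue before tumor assessment as non-responders.

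**The concern.** Membership depends on treatment received after the first injection. A treated subject who misses an administration, or who completes the injections but gets no infusion, leaves the ORR denominator. If this happens through poor tolerance or decline, the subject is unlikely to have responded. The protocol points the same way. Section 4.2 says "Subjects who do not receive all three administrations of Ad/PNP will not receive F-araAMP", and section 5.1 reports that vector alone had little effect on tumor size in nonclinical studies and that F-araAMP is not effective in solid tumors. Such exclusions can therefore raise ORR without any selection on response itself.

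Efficacy is secondary throughout, but the denominator feeds a stated decision, the 3-response threshold. If the evaluable set is appreciably smaller than the treated set, a reader of the planned tables sees only the more favorable ratio.

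Two features leave the boundary of the set open. SAP section 4 does not say whether the three administrations must fall in one cycle. Protocol 4.2 also says that subjects without all three full doses may be eligible for subsequent F-araAMP at the investigator's discretion, which sits uneasily with the sentence quoted above. The two statements must be reconciled, because they affect who is evaluable.

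**Working it through.** **Inputs.** From protocol 12.1 and SAP 3.3: 10 evaluable; 10 to 20 in the safety population; null ORR 10%; alternative 40%; reject at 3 or more responses; one-sided exact binomial test, target alpha 10%. From SAP 6.2.2.1: two-sided 95% Clopper-Pearson intervals. The documents give no rate of non-evaluability, so the number treated, N, is varied over the planning range with 10 evaluable held fixed.

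**The plan's own figures.** With X binomial on n = 10:
- Alpha = P(X ≥ 3 | 0.10) = 1 − (0.3487 + 0.3874 + 0.1937) = 0.0702. The plan states 7%.
- Power = P(X ≥ 3 | 0.40) = 1 − (0.0060 + 0.0403 + 0.1209) = 0.8327, adding the unrounded terms. The plan states 83%.

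Both reproduce.

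**Share that could be excluded.** 1 − 10/N: 0% at N = 10, 16.7% at 12, 33.3% at 15 and 50% at 20.

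**ORR at the threshold.** Assume 3 responders, all evaluable, with every excluded subject a non-responder. This is the worst case for each N. The all-treated ORR is 3/N, so the evaluable ORR is N/10 times as large. The p-value is P(X ≥ 3 | N, 0.10).

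| Treated N | ORR | 95% CI | One-sided p vs 10% |
|---|---|---|---|
| 10 (none excluded) | 3/10 = 30.0% | 6.7–65.2% | 0.070 |
| 12 | 3/12 = 25.0% | 5.5–57.2% | 0.111 |
| 15 | 3/15 = 20.0% | 4.3–48.1% | 0.184 |
| 20 (extreme) | 3/20 = 15.0% | 3.2–37.9% | 0.323 |

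The ratio of evaluable to all-treated ORR is 1.2 at 12 treated, 1.5 at 15 and 2 at 20.

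**Chance of passing the threshold.** Suppose the true all-treated ORR is 10% and all responders fall among the 10 evaluable. The rate in that set is then 0.10 × N/10, that is 10%, 12%, 15% and 20% for N = 10, 12, 15 and 20. P(X ≥ 3 | 10, that rate) is 0.070, 0.109, 0.180 and 0.322.

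**When membership is settled.** Protocol 4.2 places the three administrations on Days 1 and 2 and the first infusion on Day 3. One infusion is enough to qualify. The first on-study imaging is on Day 14 ± 2 (protocol 9.2.5). For a subject treated on schedule, membership is therefore fixed before any imaging response is known, and stopping after the first infusion does not remove the subject.

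**The case against.** The case for leaving the plan alone has real force. The evaluable set is prespecified in the protocol, and the SAP only implements it. All efficacy is secondary. On schedule the entry rule is met by about Day 3 of cycle 1, so few subjects may fail it. In Phase 1 (protocol 2.3), three injections and three days of infusion were given to 12 subjects and none discontinued. Some of the 10 to 20 enrolled may be screen failures, since the SAP counts as enrolled anyone who consents. The table above also assumes that every excluded subject is a non-responder.

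Most of this stands, and it rules out several stronger inferences that a reader might draw:

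- **That half of the treated subjects are expected to drop out of the analysis.** Half is the extreme of a planning range. It is arithmetically possible because the range is also applied to the safety population, but no document gives it as a rate.
- **That the population selects on response.** On schedule it cannot select on imaging response. The route to bias is early stopping linked to tolerance or prognosis.
- **That PFS and OS are also biased favorably.** This is not shown. SAP 6.2.2.2 censors a living subject with no adequate assessment at the first injection date, so adding such subjects leaves the PFS curve essentially unchanged. Either endpoint would shift only if excluded subjects had earlier progression or death, on which the documents are silent.
- **That the excluded subjects appear nowhere.** They are in all safety tables. SAP 6.1.1 also tabulates population sizes and discontinuation reasons and lists population membership by participant.

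Those counts and listings would let a careful reader approximate an all-treated ORR. That does not replace a prespecified analysis when a go-forward threshold rests on the ratio.

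**Conclusion.** The point holds as a gap with a low-cost remedy. All efficacy results use only subjects who meet a post-dosing treatment rule, and no supportive analysis covers all treated subjects, so ORR can be inflated. The size depends on an exclusion rate that the documents do not give. With 10 evaluable and excluded subjects counted as non-responders, 30% at the threshold becomes 25% with 12 treated, 20% with 15 and 15% at the extreme of 20. With no exclusions there is no effect. The figures are upper bounds on the distortion for each N, not forecasts. The conclusion concerns response rates only; no direction is claimed for PFS or OS. The evaluable set can properly remain primary.

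**What to change.** In SAP 6.2, keep the Efficacy Evaluable Population as primary and add:

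1. Supportive BOR, ORR and durable response rate in the Safety Population, for injected tumors and overall, with the same Clopper-Pearson intervals. Treated subjects without a post-baseline assessment count as non-responders.
2. The number of treated subjects excluded from the evaluable set, with the reason for each.
3. Optionally, PFS and OS in the Safety Population under the existing censoring rules, with no claim about direction.

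State in SAP section 4 whether the three administrations must fall within one cycle. Reconcile the two statements in protocol 4.2 on F-araAMP after incomplete Ad/PNP dosing, so that membership can be determined without ambiguity.

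The cost is one repeated set of tables and a possibly lower supportive ORR. If few subjects are excluded, the two sets of results will nearly coincide.

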## 5 GENERAL CONSIDERATIONS

### 5.1 General Data Handling

All analyses will be conducted based on SAS 9.4 or higher.

Study data will be recorded in eCRFs for all screened and enrolled participants. The electronic data capture (EDC) vendor for this study is Allucent.

The protocol deviation data will be provided in spreadsheet format from the clinical trial management system (CTMS).

Analysis tables will be presented in aggregate (overall) for a specified population.

Data will be presented in by-participant data listings. Unless otherwise stated, all listings will be sorted by site ID, participant number, and assessment date (and time, if available).

Continuous data will be summarized by treatment group based on n, mean, median, standard deviation (STD), first quartile (Q1), third quartile (Q3), minimum value, and maximum value.

Categorical data will be summarized by treatment arm using frequency counts and percentages. Where applicable, 95% confidence intervals (CIs) will be provided. Unless otherwise stated, the denominator of percentages will be the number of participants in the population or the number with non-missing data.

- The number of missing values will be presented as a separate category with no percentage, but only if one or more participants are missing data.
- Counts of zero will be presented without percentages.

Relative to the number of digits after the decimal in the raw data, summary statistics will have the following number of digits after the decimal:

- Minimum and Maximum: same number of significant digits as the raw data
- Mean, Median, Q1, and Q3: one additional significant digit
- Standard Deviation (STD) or Standard Error (SE): two additional significant digits
- Percentages <100% will be reported to one decimal place and percentages of 100% will be reported with no decimal place.
- P-values will be reported to four decimal places. If the value is below 0.0001 it will be noted as < 0.0001; if the value is above 0.9999 it will be noted as > 0.9999.
- Summary statistics will not exceed four digits after the decimal. Some laboratory parameters or other data may require judicious deviation from this rule.

Unless otherwise noted, statistical inference will be based on a 2-sided 5% significance level.

All data up to the time of study completion/withdrawal from the study will be included in the analysis, regardless of duration of treatment.

Numbering for data displays will be based on ICH E3.

## 5.2 General Definitions

Variable	Definition
Study Day	

• Study Day = date of interest - reference date + 1, when the date of interest <math>\geq</math> reference date;

• otherwise, Study Day = date of interest - reference date.

 
Note: if either day is missing, reference date calculations will not be performed. Should imputation be performed, then Study day may be computed, where appropriate.

Baseline	Defined as the last non-missing value collected prior to receiving the first intratumoral injection (based on date and time of administration as applicable).
Post-baseline	Defined as values collected after receipt of first intratumoral injection (based on date and time of administration as applicable)
Change from Baseline	Defined as: Post-baseline value - Baseline value

Percent Change from Baseline	Defined as: (Post-baseline value - Baseline value)/Baseline value x 100.  Note: To calculate percent change from baseline, the baseline value cannot be equal to zero.
Most Extreme Change	The maximum most extreme change will be based on the maximum post-baseline value; the minimum most extreme change will be based on the smallest post-baseline value. For laboratory data assessed with CTCAE grading, data from scheduled or unscheduled visits will be utilized.
Maximum Reduction from Baseline	The maximum reduction from baseline will be based on the minimum post-baseline value collected and calculated per the change from baseline formula above. For tumor measurements, post-baseline values will be considered until an overall response of PD; measurements collected after start of new cancer therapies will not be included.
Maximum Percent Reduction	Defined as the percent change that is associated with the minimum most extreme change (i.e., the largest decrease from baseline). For tumor measurements, the maximum percent reduction will be the percent change from baseline for the maximum reduction from baseline.
Maximum Percent Increase	Defined as the percent change that is associated with the maximum most extreme change.
Duration on Study (in days)	End of study date - informed consent date +1.
Duration of Time from Initial Diagnosis to Informed Consent (in months)	(Date of Informed Consent - Date of Initial Diagnosis +1) / 30.4375.
Duration of Adverse Event (in days)	
 
Stop date of event - start date of event + 1, if time is not collected.
 
(Stop date/time of event - start date/time of event)/24, if time is collected.
 

Time to Event (in months)	(Date of event - first intratumoral injection +1) / 30.4375. If the event does not occur, participant will be censored as described for the appropriate endpoint in section 6.2.
Reporting in Months	Divide number of days by 30.4375
Reporting in Years	Divide number of days by 365.25
Reporting in Weeks	Divide number of days by 7
Height (in cm)	= height (in inches) * 2.54
Weight (in kg)	= weight (in lbs) * 0.4536
BMI (kg/m  )	= weight(kg)/[height(m)  ]
Age (yr)	Age is collected in the EDC system (or through the IXRS system)

### 5.3 Data Imputation Rules

Generally, missing data will not be imputed, and will be presented as collected in the study database.

In cases where adverse event or medication dates are missing, the imputation methods described in Appendix 1 will be used to determine flags for treatment-emergent events and concomitant medications.

Conventions for censoring for time-to-event efficacy endpoints are described within the definitions of the endpoints in section 6.2.2.

### 5.4 Visit Windows

Both efficacy and safety endpoints will be analyzed according to the recorded scheduled visits. Unscheduled visits will not be summarized in tables but will be presented in data listings.

### 5.5 Pooling of Sites/Centers

Not Applicable.

## 6 ANALYSIS METHODS

### 6.1 Study Participant Data

#### 6.1.1 Participant Enrollment and Disposition

Participant enrollment and disposition data will be summarized for the enrolled population and listed. Enrollment and disposition summaries will include:

- Number of participants in each analysis population
- Number of participants who have discontinued the study
- Primary reason for early withdrawal/discontinuation from study
  - Progressive disease
  - Adverse Event
  - Withdrawal by Subject
  - Lost to follow-up
  - Protocol Specified Withdrawal Criterion Met
  - Protocol Violation
  - Physician Decision
  - Pregnancy
  - Non-Compliance with Study Drug
  - Non-Compliance with Study Schedule
  - Study Terminated by Sponsor
  - Site Terminated by Sponsor
  - Sponsor Request
  - Death
  - Other

- Is early withdrawal/discontinuation from study related to COVID-19?
- Time (months) on study
- Primary reason for early withdrawal/discontinuation from treatment
  - Progressive disease
  - Adverse Event
  - Withdrawal by Subject
  - Lost to follow-up
  - Protocol Specified Withdrawal Criterion Met
  - Protocol Violation
  - Physician Decision
  - Pregnancy
  - Non-Compliance with Study Drug
  - Non-Compliance with Study Schedule
  - Study Terminated by Sponsor
  - Site Terminated by Sponsor
  - Sponsor Request
  - Death
  - Other
- Is early withdrawal/discontinuation from treatment related to COVID-19?

Completion of treatment is defined as participants who have received at least three administrations of Ad/PNP and at least 1 infusion of F-araAMP prior to their withdrawal from the study.

Completion of the study is defined as any participant who completes one or more cycles (visits 1-7).

Participants who are discontinued from the study via the discretion of the investigator, or no longer receiving IP by other criteria specified in the protocol, will be considered to have completed the study if at least 1 cycle (visits 1-7) is completed.

Participants who withdraw from the study will be considered to have completed the study if at least 1 cycle (visits 1-7) is completed.

Participants contributing to each analysis population and final disposition status will be listed.

### 6.1.2 Protocol Deviations

A listing of protocol deviations will be provided.

### 6.1.3 Demographic and Baseline Characteristics

Participant demographics will be summarized and listed. These will include age, sex (Male / Female), child-bearing potential (Yes / No), ethnicity (Hispanic / Non-hispanic / Not Reported / Unknown), race (American Indian or Alaska Native / Asian / Black or African American / Native Hawaiian or Pacific Islander / White / Not Reported), baseline height (cm), baseline weight (kg), and baseline BMI (kg/m^2).

Disease history and baseline disease characteristics will be summarized. These will include: Duration of time from initial diagnosis to screening (in months), primary site of cancer, histology type, stage at diagnosis, TNM at study entry, Progression/Recurrence/Metastasis observed after diagnosis, Progression/Recurrence/Metastasis specification and location, extent of disease, baseline tumor measurements, prior chemotherapy (Yes/No), prior immunotherapy (Yes/No), prior radiation (Yes/No), prior surgery (Yes/No), baseline ECOG, Chest Radiograph results, baseline CT scan/MRI results will be summarized, as well as baseline prognostic laboratory values for the following selected laboratory tests:

- Hemoglobin, hematocrit, white blood cell count, lymphocytes (absolute), lymphocytes (percentage), neutrophils (absolute), neutrophils (percentage), platelet count.
- Prothrombin time (PT), activated partial thromboplastin time (aPTT), international normalized ratio (INR).

Listings of demographics, disease history, baseline disease characteristics, and Smoking/Alcohol History will be provided.

